4.1.1. Dose Escalation Phase (Phase 1b)

The Phase 1b, dose escalation phase consists of the following:

Arm A: Pamiparib (60 mg BID) administered continuously at increasing exposures of 2, 4, and 6 weeks in combination with RT administered for 6 to 7 weeks.

Arm B: Depending on the safety of the Arm A combination, the following combination may be explored: pamiparib (at the exposure determined as safe in Arm A) in combination with RT administered for 6 to 7 weeks and increasing doses of TMZ ([Section 4.2.1](#)).

In both Arms A and B, after RT is completed, patients will receive no further RT.

Maintenance Treatment for Arms A and B

Following completion of RT, at the discretion of the investigator and after discussion with the medical monitor, patients in the Arm A escalation and expansion and patients in Arm B escalation phases of the study may continue to receive pamiparib in combination with TMZ. TMZ will be given at a dose level lower than or equal to a dose that has been determined to be safe and tolerable in Arm C of study.

In the Arm B expansion phase of the study, maintenance treatment with pamiparib in combination with TMZ will be mandatory for all patients.

Dosing for this maintenance treatment should begin after the 4-week rest period (+ 7 days) to allow for recovery from RT treatment (please refer to [Appendix 1 Table 4](#)).

Arm C: Pamiparib (60 mg BID, administered continuously) in combination with increasing doses of TMZ ([Section 4.2.1](#)). TMZ will be administered on Days 1 to 21 of each 28-day cycle.

Approximately 60 patients may be enrolled in the 3 arms of the dose escalation phase. The actual sample size in this phase will depend on the number of dose escalation cohorts enrolled per arm.

4.1.2. Dose Expansion Phase (Phase 2)

Once the safety, tolerability, PK, pharmacodynamic, and preliminary antitumor activity have been reviewed for the dose escalation cohorts of each of the arms, up to approximately 60 patients may be enrolled in expansion cohorts for each of the 3 arms at a dose level below or equal to the MTD or MAD for that arm. In Arm C, 2 expansion cohorts may be opened, one for unmethylated GBM and one for methylated GBM ([Section 4.3](#)).

Approximately 60 patients may be enrolled during the dose escalation phase, and in each of the 4 dose-expansion cohorts totalling 240 patients in the dose expansion phase, for an approximate total of 300 patients enrolled in the entire study.

Adverse events (AEs) during and after the treatment period with study drug(s) will be followed and documented as outlined in [Section 8.4](#) and [Section 10](#). AEs will be graded according to National Cancer Institute Common Toxicity Criteria for Adverse Events (NCI-CTCAE) v4.03.

To determine the PK properties of pamiparib, blood samples will be taken at various time points as outlined in [Section 8.5](#) and [Appendix 1](#). To determine pharmacodynamic effects of pamiparib, blood samples will be obtained coinciding with specific PK time points as outlined in [Section 8.5](#) and [Appendix 1](#).

Disease status will be assessed using Response Assessment in Neuro-Oncology (RANO) criteria ([Appendix 2](#)). Patients will undergo tumor assessments at screening and then every 8 weeks, or as clinically indicated.

In Arm B expansion phase of the study, maintenance treatment (pamiparib in combination with TMZ) will be mandatory for all patients. In Arm A expansion phase of the study, continuation of treatment (with pamiparib in combination with TMZ) will be at the discretion of the investigator after discussion with the Medical Monitor.

Following completion of RT, all patients in Arms A and B who continue on pamiparib in combination with TMZ should follow the schedule of assessments for maintenance treatment ([Appendix 1 Table 4](#)).

Patients in Arms A and B who have completed all study treatments per protocol and do not continue on pamiparib in combination with TMZ (maintenance) should have their EOT visit at the end of the Rest Phase, 28 days after RT was completed, unless they do not complete the full study treatment; in such a case, they should have the end-of-treatment (EOT) visit within 7 days of stopping all study treatment.

All other patients who have discontinued all study treatments should return to the clinic for an EOT visit within 7 days of stopping all study treatment. A visit should be scheduled as soon as possible, but the EOT visit may occur later after discussion with the medical monitor for specific circumstances, such as prolonged hospitalization.

After the EOT visit, all patients should have regular follow-up for safety, efficacy, and survival as outlined in [Section 6.6](#).

Study procedures and assessments are further detailed in [Section 8](#).

4.2. Details of Dose-Escalation Stage

4.2.1. Starting Dose and Dose-Escalation Approach

Arm A

RT will be administered QD × 5 days/week for 6 to 7 weeks with 1.8 or 2 Gy/fraction for a total target dose of between 58 Gy and 64 Gy.

The starting dose for pamiparib will be the 60 mg PO BID based on the rationale outlined in [Sections 1.3](#) and [1.4](#). In Cohort 1, exposure to pamiparib will be limited to the first 2 weeks of RT. In Cohorts 2 and 3, pamiparib will be given for the first 4 and 6 weeks of RT, respectively. If 2, 4, or 6 weeks of combination treatment exceeds the MTD, alternative regimens for pamiparib may be explored after discussions with all investigators based on which regimen exceeded the MTD and

what toxicities were observed. For example, if 2 weeks of pamiparib are not tolerated, a schedule of 1 week on, 1 week off, or 1 week on and 3 weeks off may be explored. Depending on data available at that time, a lower dose level of pamiparib may also be explored.

Arm B

The opening of Arm B will depend on the safety of the Arm A combination, and Arm B may be enrolled at the initial dose and schedule of pamiparib found to be safe and tolerable in Arm A. RT will be administered as for Arm A.

The first dose level of TMZ will be lower than or equal to a dose that has been determined to be safe and tolerable in Arm C, and dose escalation will proceed as described for Arm C. The time period of TMZ administration may be the same or shorter than that for pamiparib administration. Similar to Arms A and C, alternative regimens may be explored with adjustments of dose and/or schedule as outlined for Arms A and C.

Arm C

Since TMZ is given as a DNA-damaging sensitizer for pamiparib and to simplify TMZ dosing, flat-dosing will be used for TMZ. The first dose level of 40 mg QD corresponds to 23 mg/m^2 assuming an average body surface area of 1.73 m^2 . Subsequent dose levels of 80 mg and 120 mg correspond to 46 mg/m^2 and 69 mg/m^2 , respectively. Additional higher dose levels may be explored, and the TMZ dose will not be increased by more than 50% each time. TMZ will be given on Days 1 to 21 of each 28-day cycle based on data and rationale discussed in [Sections 1.2, 1.3, and 1.4](#).

Following the same rationale for pamiparib dosing as for Arms A and B, all patients will receive pamiparib of 60 mg PO BID continuously. If the MTD is exceeded for a combination regimen that is considered inadequate for further exploration based on all data available at that time, alternative regimens may be explored, such as a lower dose of pamiparib, a lower dose of TMZ, and/or alternative dosing schedules for either drug.

Depending on emerging safety data from this and other pamiparib Phase 1 studies, the pamiparib regimen may be switched to QD for one or more of the 3 arms at any time during or after dose escalation. The QD dose of pamiparib may be escalated according to the dose escalation rules in [Section 4.2.2](#) of the protocol.

Once Arm C dose escalation identifies the RP2D for the combination, that combination regimen may be applied in Phase 2 Arm A and B patients (see [Section 4.3](#)). Additionally, data emerging from other ongoing studies with pamiparib may be used to determine the combination regimen.

4.2.2. Rules for Dose Escalation

Dose escalation in all 3 arms will occur in accordance with the following modified 3+3 dose escalation rules.

A minimum of 3 patients will be initially enrolled per cohort.

- If none of the first 3 evaluable patients enrolled in a given cohort experience a DLT, dose escalation may proceed.
- If one of the first 3 evaluable patients enrolled in a given cohort experiences a DLT, additional patients (for a minimum of 6 evaluable patients) will be enrolled in that cohort.
 - If less than one-third of evaluable patients in a given cohort experiences a DLT (eg, DLTs in fewer than 2 of 6 patients), escalation will proceed to the next higher dose level.

If a DLT is observed in one-third or more of patients (eg, 2 or more of up to 6 patients), the MTD will have been exceeded, and dose escalation will be stopped.

1. Additional patients (for a minimum of 6 evaluable patients) will then be assessed for DLTs at the preceding dose level (if a minimum of 6 evaluable patients had not already been assessed at that dose level).
2. If the MTD is exceeded at a given dose level, a lower or intermediate dose level may be assessed for toxicity in the same manner as described above.

If the MTD is exceeded at a given dose level, the next highest dose level at which less than one-third of evaluable patients in a given cohort experiences a DLT (eg, DLTs in fewer than 2 of 6 patients) will be declared the MTD.

If less than one-third of evaluable patients (eg, DLTs in fewer than 2 of 6 patients) at the highest dose level experience a DLT, this dose level will be declared the MAD.

Available data relevant for dose-escalation decisions for pamiparib (Arm A) or TMZ (Arms B and C), including AEs, laboratory assessments, and PK analyses (as available), will be reviewed by the medical monitor, PK scientist, Safety Scientist and Biostatistician with input from other members of the team as appropriate. On the basis of a review of these data and in consultation with the investigators, a determination will be made as to the next appropriate dose escalation step.

4.2.3. Assessment of Dose-Limiting Toxicity

Dose-limiting toxicities will be assessed during the DLT assessment window starting with the first day of study treatments for all cohorts. The following assessments must be obtained at the end of the DLT assessment window: complete physical examination, vital signs and weight, Eastern Cooperative Oncology Group (ECOG) performance status, ECG, hematology, chemistry, coagulation, urinalysis, AEs, and concomitant medications.

For Arm A, the DLT assessment window will depend on the time period of pamiparib administration during RT and will consist of the time period of combination treatment plus 4 weeks after the last scheduled combination treatment, eg, 6 weeks for Cohort 1 of Arm A when pamiparib is given during the first 2 weeks of RT, and 10 weeks for Cohort 3 of Arm A when pamiparib is given during 6 weeks of RT.

For Arm B, the DLT assessment window will depend on the time period of combined administration of pamiparib and TMZ during RT and will otherwise follow Arm A rules, eg, if TMZ will be given only for the first 3 weeks of pamiparib and RT, then the DLT assessment window will be 7 weeks.

For Arm C, the DLT assessment window will encompass the first cycle of 28 days.

Patients who withdraw or are withdrawn from the study prior to completing the DLT assessment window for reasons other than a DLT will not be considered evaluable for DLT and will be replaced if needed to meet patient number requirement for dose escalation. Patients who do not experience a DLT and who do not receive ≥ 42 Gy of RT (Arms A and B) and $\geq 70\%$ of scheduled pamiparib (Arms A, B and C) and TMZ (Arms B and C) dosing during the DLT assessment window will not be considered evaluable for DLTs and will be replaced if needed to meet patient number requirement for DLT assessment.

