4.2.4. Definition of Dose-Limiting Toxicity

A DLT is defined as one of the following toxicities occurring during the DLT assessment window (as defined for each of the arms and cohorts; [Section 4.2.3](#)) and considered by the investigator to be related to pamiparib:

- Grade ≥ 3 non-hematologic, non-hepatic major organ AE, with the following exceptions:
 - Grade 3 nausea, vomiting, or diarrhea that resolves to Grade ≤ 1 with optimal medical management within 3 days
 - Grade 3 electrolyte disturbances that respond to correction within 3 days
- Grade 4 neutropenia lasting > 7 days
- Grade ≥ 3 febrile neutropenia
- Grade 3 thrombocytopenia with clinically significant bleeding
- Grade 4 thrombocytopenia lasting > 3 days and requiring transfusion, or any decreased platelet count $< 15,000/\text{mm}^3 / < 15.0 \times 10^9/\text{L}$
- Grade ≥ 4 anemia
- Grade ≥ 3 total bilirubin or hepatic transaminases (ALT [SGPT] or AST [SGOT]) with the following exceptions:
 - For patients with Grade 1 hepatic transaminase levels at baseline, a hepatic transaminase level of $> 7.5 \times$ upper limit of normal (ULN) will be considered a DLT.

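### If Arm B TMZ runs shorter than pamiparib, the Arm B DLT window closes before the Arm A window for the same pamiparib + RT exposure

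*Protocol*

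**What the plan says.** Protocol Section 4.2.3 gives each arm its own window. In Arm A it "will consist of the time period of combination treatment plus 4 weeks after the last scheduled combination treatment", with two worked cases: 6 weeks for Cohort 1, and "10 weeks for Cohort 3 of Arm A when pamiparib is given during 6 weeks of RT".

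In Arm B the anchor changes: "the DLT assessment window will depend on the time period of combined administration of pamiparib and TMZ during RT", and Arm A rules apply otherwise. The worked case is "if TMZ will be given only for the first 3 weeks of pamiparib and RT, then the DLT assessment window will be 7 weeks".

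Two texts allow the courses in Arm B to differ in length. Section 4.2.1 says: "The time period of TMZ administration may be the same or shorter than that for pamiparib administration". Section 4.1.1 carries into Arm B "pamiparib (at the exposure determined as safe in Arm A) in combination with RT administered" for 6 to 7 weeks. The Arm A exposures are 2 weeks in Cohort 1, and "In Cohorts 2 and 3, pamiparib will be given for the first 4 and 6 weeks of RT, respectively".

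One text points the other way. Footnote o of Appendix Table 2 (the Arm B schedule of assessments) has TMZ follow pamiparib's schedule.

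Under Section 4.2.4 an event is a DLT only if it falls inside the window and is "considered by the investigator to be related to pamiparib". Section 4.2.2 bases the modified 3+3 decision on the DLT count and adds a review of AEs, laboratory data and available PK. The SAP (Sections 6.1 and 6.5.2) uses the DLT window without redefining it.

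**The concern.** The DLT definition is about pamiparib, but the Arm B window does not follow pamiparib. When TMZ stops first, the window shortens by the difference between the two courses, while pamiparib and RT go on. The same pamiparib-related event, equally late, would then be a DLT in Arm A and not in Arm B, whose patients have also received TMZ. Protocol Sections 1.5 and 7.1.5.3 themselves expect overlapping toxicity from these treatments.

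Some criteria in Section 4.2.4 also need time to be met. Grade 4 neutropenia must last more than 7 days, so an episode that begins in week 7 cannot qualify before a week-7 close. Section 4.2.3 does not say how to classify an event that straddles the close.

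The Arm B DLT count feeds TMZ escalation and the MTD or MAD of TMZ with RT, which is a Phase 1b primary objective.

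**Working it through.** **1. Reproduce the stated windows.** Window = weeks of the defining combination + 4.

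- Arm A Cohort 1: 2 + 4 = 6 weeks (stated: 6).
- Arm A Cohort 3: 6 + 4 = 10 weeks (stated: 10).
- Arm B example: 3 + 4 = 7 weeks (stated: 7).

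All three agree.

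**2. Compare the arms at equal pamiparib exposure.** TMZ is never longer than pamiparib, so the overlap equals the TMZ period. The Arm B window is TMZ weeks + 4, and the Arm A window is pamiparib weeks + 4. Follow-up after the last pamiparib dose in Arm B is TMZ weeks + 4 − pamiparib weeks.

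| Pamiparib (wk) | TMZ (wk) | Arm A window | Arm B window | Difference | Arm B weeks after last pamiparib |
|---|---|---|---|---|---|
| 4 | 3 | 8 | 7 | 1 | 3 |
| 4 | 4 | 8 | 8 | 0 | 4 |
| 6 | 3 | 10 | 7 | 3 | 1 |
| 6 | 4 | 10 | 8 | 2 | 2 |
| 6 | 6 | 10 | 10 | 0 | 4 |

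The difference is always pamiparib weeks − TMZ weeks. RT of 29 to 33 fractions at 5 per week lasts 29/5 = 5.8 to 33/5 = 6.6 weeks, so a 7-week window closes at about the end of RT.

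**3. What the 6/3 window covers.** The last triple-combination dose is at week 3, and weeks 4 to 7 are the 4 weeks after it. Weeks 8 to 10, which follow continued pamiparib + RT, are left out.

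**4. Illustrative effect on escalation.** None of the risks or timings in this step comes from the documents. Escalation is taken to follow 0 DLTs in 3 patients, or 1 in 3 and then none in 3 more. With p the DLT probability inside the window and q = 1 − p:

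P(escalate) = q³ + 3pq² × q³

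- True 10-week risk 30%, constant hazard: h = −ln(0.70)/10; 7-week risk = 1 − exp(−7h) = 22.1%. P(escalate) is 0.494 at p = 0.30 and 0.663 at p = 0.221.
- True risk 40%, same method: 7-week risk 30.1%. P(escalate) goes from 0.309 to 0.493.

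A constant hazard places (30 − 22.1)/30 = 26% of the DLTs in weeks 8 to 10 in the first case. Varying that share directly:

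| True 10-week risk | Share of DLTs in weeks 8–10 | P(escalate), 10-week count | P(escalate), 7-week count |
|---|---|---|---|
| 30% | 20% to 50% | 0.49 | 0.62 to 0.81 |
| 33% | 10% to 40% | 0.43 | 0.50 to 0.71 |
| 40% | 10% to 40% | 0.31 | 0.38 to 0.62 |

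If no DLTs fall in weeks 8 to 10, nothing changes.

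**5. Visits at the close of the window.** Section 4.2.3 requires, among other tests, an ECG and coagulation at the end of the window. In Appendix Table 2, coagulation after screening appears only at EOT (Day 71–78), and the last ECG before EOT is Day 36. No visit near week 7 has both; the EOT visit does, and it matches a 10-week close. At week 8 the nearest visit, Rest Day 15 (Day 57–64), has no ECG, chemistry, coagulation, urinalysis or complete physical examination.

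**The case against.** The best defence is that Arm B asks a question about TMZ. Its pamiparib exposure has already been judged safe in Arm A, where 6 weeks with RT would have been watched for 10 weeks. Following the triple combination for 4 weeks applies the Arm A principle to the added drug. The protocol makes no formal comparison of DLT fractions between the arms. Closing near the end of RT is not peculiar to Arm B either: the Arm A Cohort 1 window closes at 6 weeks. This is a coherent rationale. It does not fully answer the point, because Arm A cannot show how continued pamiparib + RT is tolerated after a course of TMZ, and Arm A Cohort 1 still has 4 weeks after its last pamiparib dose.

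A reader might infer that late DLTs of the triple regimen go unobserved. The documents do not support that. The 7-week window covers 4 weeks after the last triple-combination dose. Later toxicity is still reported as AEs until 30 days after the last study treatment or the start of new anticancer therapy, whichever comes first (Section 10.3.1). Section 4.2.2 also has AE and laboratory data reviewed before each escalation step. This mitigates the gap without closing it: the review is a matter of judgement, whereas the DLT count is the stated criterion.

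Three further limits stand. Six weeks of pamiparib with 3 of TMZ lies within what the protocol permits but is not a named Arm B cohort. If footnote o governs, the windows are equal and the gap disappears. And the SAP (Sections 5 and 8) reports Phase 1b enrolment of 46 patients and no Arm B expansion cohort, so the Arm B dose fed no expansion in that arm.

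**Conclusion.** The point holds in conditional form. If TMZ is shorter than pamiparib in Arm B, the window is shorter than the Arm A window for the same pamiparib + RT exposure by exactly the difference between the courses. In the 6/3 case that is 3 weeks, leaving 1 week after the last pamiparib dose instead of 4. The direction needs no assumption, since a shorter window cannot count more events.

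The effect on escalation (about 49% to 66% at a 30% ten-week risk) is an illustration only. Constant hazard is a strong assumption when TMZ stops at week 3 and pamiparib and RT stop at about weeks 6 to 7. Nothing in the documents shows that an over-toxic TMZ level was passed, or that Arm B was always watched for less time than Arm A. The disagreement over the TMZ period, between Sections 4.2.1 and 4.2.3 and footnote o of Appendix Table 2, stands whatever the size of the effect.

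**What to change.** First reconcile Sections 4.2.1 and 4.2.3 with footnote o of Appendix Table 2 on the length of the Arm B TMZ course. If TMZ may be shorter than pamiparib, define the Arm B window as Day 1 to 4 weeks after the last scheduled day on which either drug is given with RT, and replace the 7-week example. The window is then never shorter than the Arm A window for the same pamiparib schedule.

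The cost is protocol wording and a longer wait per cohort, equal to the pamiparib course minus the TMZ course: 3 weeks for 6/3, 1 week for 4/3, none when they are equal. For a 10-week window the end-of-window tests fall at the existing EOT visit. For other lengths, such as 8 weeks, the missing tests must be added to a visit, as is already needed for the current 7-week window.

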4.2.4. Definition of Dose-Limiting Toxicity

A DLT is defined as one of the following toxicities occurring during the DLT assessment window (as defined for each of the arms and cohorts; [Section 4.2.3](#)) and considered by the investigator to be related to pamiparib:

- Grade ≥ 3 non-hematologic, non-hepatic major organ AE, with the following exceptions:
 - Grade 3 nausea, vomiting, or diarrhea that resolves to Grade ≤ 1 with optimal medical management within 3 days
 - Grade 3 electrolyte disturbances that respond to correction within 3 days
- Grade 4 neutropenia lasting > 7 days
- Grade ≥ 3 febrile neutropenia
- Grade 3 thrombocytopenia with clinically significant bleeding
- Grade 4 thrombocytopenia lasting > 3 days and requiring transfusion, or any decreased platelet count $< 15,000/\text{mm}^3 / < 15.0 \times 10^9/\text{L}$
- Grade ≥ 4 anemia
- Grade ≥ 3 total bilirubin or hepatic transaminases (ALT [SGPT] or AST [SGOT]) with the following exceptions:
 - For patients with Grade 1 hepatic transaminase levels at baseline, a hepatic transaminase level of $> 7.5 \times$ upper limit of normal (ULN) will be considered a DLT.

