2. STUDY OBJECTIVES

2.1. Primary Objectives

2.1.1. Phase 1b

Arm A (pamiparib + RT): Patients with first-line glioblastoma with unmethylated *MGMT* promoter (unmethylated GBM)

- To assess safety and tolerability of pamiparib combined with RT
- To identify DLTs and determine the MTD or maximum administered dose (MAD) for pamiparib combined with RT
- To select the recommended Phase 2 schedule for pamiparib combined with RT

Arm B (pamiparib + RT + TMZ): Patients with first-line unmethylated GBM

- To assess safety and tolerability of pamiparib combined with RT and TMZ
- To identify DLTs and determine the MTD or MAD for TMZ when combined with RT and the MTD/MAD of pamiparib as determined in Arm A
- To select the RP2D for TMZ when combined with RT and the MTD/MAD of pamiparib determined in Arm A

Arm C (pamiparib + TMZ): Patients with recurrent/refractory GBM

- To assess safety and tolerability of pamiparib combined with TMZ
- To identify DLTs and determine the MTD or MAD for TMZ combined with pamiparib
- To select the RP2D for TMZ combined with pamiparib

2.1.2. Phase 2

Arm A, Expansion 1 (pamiparib + RT): Patients with first-line unmethylated GBM

- To make a preliminary assessment of efficacy of pamiparib combined with RT

Arm B, Expansion 1 (pamiparib + RT + TMZ): Patients with first-line unmethylated GBM

- To make a preliminary assessment of efficacy of pamiparib combined with RT and TMZ

Arm C, Expansion 1 (pamiparib + TMZ): Patients with recurrent/refractory unmethylated GBM

- To make a preliminary assessment of efficacy of pamiparib combined with TMZ

Arm C, Expansion 2 (pamiparib + TMZ): Patients with recurrent/refractory methylated GBM

- To make a preliminary assessment of efficacy of pamiparib combined with TMZ

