4.3. Details of Cohort-Expansion Stage

Expansion cohorts (up to approximately 60 patients each) may be enrolled at a dose level below or equal to the MTD or MAD of pamiparib (Arm A) or TMZ (Arms B and C) to better characterize the safety and tolerability of pamiparib in combination with RT, RT and TMZ or TMZ alone, and to make a preliminary determination of the efficacy of these combinations.

Arms A and B may have one expansion cohort each, and only patients with unmethylated GBM will be allowed to enroll. After dose escalation in Arm C for GBM patients regardless of *MGMT* methylation status, Arm C may have two expansion cohorts, one for unmethylated GBM and one for methylated GBM.

The rules for continued dosing in the cohort-expansion stage will be identical to those in the dose-escalation stage.

If the frequency of Grade ≥ 3 toxicities or other unacceptable chronic toxicities in the cohort expansion stage of a given arm suggest that the MTD has been exceeded at that dose level, any remaining accrual at that dose level will be halted. Consideration will then be given to enrolling additional patients (up to approximately 60 patients) into an expansion cohort at a lower dose level.

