7.1.1.3. Dosage and Administration

Pamiparib 60 mg will be administered PO BID, once in the morning and once in the evening. The time difference between 2 consecutive doses should be approximately 8 to 12 hours.

Patients will be instructed to swallow the capsules whole, in rapid succession, with water. Patients will be required to fast for at least 1 hour before and 2 hours after each pamiparib administration. Water is allowed during the fasting period.

A dose of pamiparib should be skipped if it is not taken within 2 hours of the scheduled time. An extra dose of pamiparib should not be taken to make up for a missed dose. If vomiting occurs during the course of treatment, no re-dosing of the patient is allowed before the next scheduled dose.

On days with PK assessments, the morning dose of pamiparib should be administered in the clinic in accordance with the schedule for PK samples ([Appendix 1](#)).

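### Arms B and C escalate TMZ, but a DLT counts only if judged related to pamiparib, so TMZ-only events drop out of the count behind the TMZ MTD/MAD; the effect is probably small, but no planned table measures it.

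*Protocol*

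**What the plan says.** Protocol 4.2.4 lists the DLT criteria once, for all arms, and admits only events "considered by the investigator to be related to pamiparib". TMZ is not named.

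In Arm C the Phase 1b primary objective is "To identify DLTs and determine the MTD or MAD for TMZ combined with pamiparib" (Protocol 2.1.1), and Arm B has a parallel TMZ objective. Pamiparib starts at 60 mg BID in Arm C while TMZ steps through 40, 80 and 120 mg (4.2.1). Under 4.2.2, once the MTD has been exceeded, the MTD is "the next highest dose level at which less than one-third of evaluable patients in a given cohort experiences a DLT". The MAD also rests on fewer than one-third of patients having a DLT.

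A patient without a counted DLT who misses the dosing threshold, which includes 70% of scheduled pamiparib and TMZ, "will not be considered evaluable for DLTs and will be replaced if needed to meet patient number requirement for DLT assessment" (4.2.3).

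The result is used later. Section 4.3 caps expansion dosing at the MTD or MAD, and maintenance TMZ in Arms A and B must be "lower than or equal to a dose that has been determined to be safe and tolerable in Arm C of study" (4.1.1). SAP 6.5.2 summarises the DLT events recorded on the AE form, by dose cohort and arm, in the DLT-evaluable set.

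**The concern.** The relatedness clause names the partner drug, not the drug being escalated. It fits Arm A, where pamiparib exposure is what increases. In Arms B and C the question is how much TMZ can be added, and an event blamed on TMZ alone bears directly on that question yet falls outside the formal count. No other passage in the protocol or SAP widens the clause for these arms, although Protocol 7.1.5.2 already refers to pamiparib and/or TMZ when it sets dose modifications.

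An uncounted event can only lower the DLT count or remove the patient from it, so any error runs toward declaring a TMZ level tolerable. At stake are the TMZ MTD/MAD and RP2D, which are primary objectives. They feed the Arm C expansion (30 patients, SAP 5) and maintenance TMZ. SAP 8 drops the Arm B expansion, so that use no longer arises.

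**Working it through.** The documents give no operating characteristics for the 3+3 rule, so there is no planned figure to reproduce.

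**Step 1: what happens to an uncounted patient.** Both drugs are held together (Protocol 7.1.5.3) and missed doses are not made up: "An extra dose of pamiparib should not be taken to make up for a missed dose" (7.1.1.3; 7.1.2.3 says the same for TMZ). The Arm C window is 28 days, with pamiparib scheduled on all 28 and TMZ on Days 1 to 21. Take full dosing before a hold that starts on day d and lasts to Day 28.

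- Pamiparib received = (d−1)/28. At d = 20 this is 19/28 = 67.9% (fails); at d = 21 it is 20/28 = 71.4% (passes).
- TMZ received = (d−1)/21. At d = 15 this is 14/21 = 66.7% (fails); at d = 16 it is 15/21 = 71.4% (passes).

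Such a hold makes the patient non-evaluable if it starts by Day 20; a later one leaves the patient in as a non-DLT. Which is more common depends on onset timing and hold length, and the documents give neither. Both cases are carried forward.

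**Step 2: effect on the rule.** Inputs from Protocol 4.2.2: 0 of 3 escalates; 1 of 3 expands to 6; fewer than 2 of 6 passes. Assumed, not in the documents: true DLT rate p (30%, 40%) and share s of DLT-grade events attributed to TMZ alone (0%, 5%, 10%). The calculation ignores the AE and laboratory review.

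- Counted rate if kept as a non-DLT: c = p(1−s).
- Counted rate if replaced: c = p(1−s)/(1−ps).
- Chance of escalating past the level: (1−c)³ + 3c(1−c)² × (1−c)³.
- Chance of 0 or 1 DLT in 6, the result that supports an MTD/MAD: (1−c)⁶ + 6c(1−c)⁵.

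Example, p = 0.40. With s = 0, c = 0.40: 0.216 + 0.432 × 0.216 = 0.309. With s = 0.10 and patients kept, c = 0.36: 0.262 + 0.442 × 0.262 = 0.378.

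| True rate p | Share s | Escalate: kept / replaced | 0–1 of 6: kept / replaced |
|---|---|---|---|
| 40% | 0% | 31% / 31% | 23% / 23% |
| 40% | 5% | 34% / 33% | 27% / 25% |
| 40% | 10% | 38% / 35% | 30% / 27% |
| 30% | 0% | 49% / 49% | 42% / 42% |
| 30% | 5% | 53% / 52% | 45% / 44% |
| 30% | 10% | 56% / 54% | 49% / 47% |

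The shift from s = 0 is about 2 to 3 points at 5% and 4 to 7 points at 10%. It stays small only while the share does: at p = 40% the chance of escalating is 45% (kept) or 40% (replaced) at a 20% share.

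**Step 3: what planned outputs would show.** SAP 6.5.2 covers recorded DLTs only. SAP 6.5.3 tabulates TEAEs of Grade 3 or above by arm and cohort, whatever the cause. That gives a rough upper bound by cohort, but it applies neither the DLT window nor the 4.2.4 criteria, such as duration, bleeding or transfusion. The treatment-related tables do not separate the drugs. The AE listings would allow the count to be rebuilt by hand.

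**The case against.** The strongest reply is that the gap opens only when the investigator excludes pamiparib. Protocol 10.1.3 treats an event as related when causation cannot be excluded, and in Arm C pamiparib is given throughout the DLT window. TMZ is there as a sensitizer (4.2.1, 7.1.5.3), so severe toxicity is naturally a combination effect. The named TMZ levels are also low: 23, 46 and 69 mg/m² equivalent, all below the 75 mg/m² schedules described in the background. This stands, and it is why the effect is probably small.

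The count is also not the only safeguard. AE and laboratory data are reviewed before each dose step (4.2.2). Expansion accrual is halted if Grade 3 or higher toxicity suggests that the MTD has been exceeded, with no relatedness condition (4.3). Expansion may run below the MTD/MAD. These points stand too, but the MTD and MAD remain defined by DLT proportions, and the expansion halt acts only after expansion patients have been exposed.

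A reader might infer from 7.1.5.3, which presumes that a Grade 3 or 4 AE more likely comes from adding TMZ, that the TMZ-only share is large. The text does not support that: it compares the combination with pamiparib on its own, which does not exclude pamiparib as a contributor.

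**Conclusion.** The point holds as a mismatch between the DLT definition and the drug being escalated. Its direction is known, toward calling a TMZ level tolerable; its size is not. The percentages illustrate sensitivity under assumed DLT rates and TMZ-only shares and are not evidence of impact; with a zero share there is no effect.

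A reader might go further and conclude that the TMZ MTD/MAD or RP2D is too high, or that TMZ toxicity goes unseen. The documents support neither. They report no uncounted event, and severe AEs of any cause are reviewed, tabulated and listed. What is missing is a planned summary showing whether the restriction changed the count in any cohort. Because the TMZ dose is a primary objective and the remedy is cheap, this should be fixed.

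**What to change.** For Arms B and C, define a DLT in Protocol 4.2.4 as related to pamiparib and/or TMZ, as 7.1.5.2 already words it. Phase 1b enrolment is complete (46 patients, SAP 5), so this cannot alter escalation decisions already made; the useful change now is in reporting.

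- Add to SAP 6.5.2 a table by dose cohort of all DLT-window events in Arms B and C that meet the 4.2.4 severity criteria, regardless of attribution, including patients excluded as non-evaluable.
- Beside the TMZ MTD/MAD and RP2D, state that the protocol DLT count was limited to pamiparib-related events.

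The cost is one descriptive table from data already planned for the listings, and possibly a less favourable tolerability statement. If the table shows no additional events, it strengthens the dose recommendation.
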